5.7 Trial treatments

Infusion of TPA and fresh frozen plasma into the perfusate during DCD liver perfusion.

5.8 Criteria for Discontinuation

5.8.1 *Individual liver*

5.8.1.1 *Transplant criteria*

Criteria favouring transplantation of liver include:

Perfusate:

- ALT < 6000 u/L

- Lactate fall to <2 in 2 hours
- Glucose falling hour on hour after 2 hours
- Producing bile
- Need for <40mls 8.4% NaHCO₃ in the first 4 hours to maintain a perfusate pH>7.2 as measured on near patient blood gas machine (not the Organox *metra* reading)

Bile

- pH>7.6
- Bile glucose <2.0mmol/L or >10mmol/L less than perfusate.

Criteria favouring non-use of liver include

Perfusate

- ALT>10000iu/L
- Lactate>2.5 at 2 hours
- Glucose failing to fall after the second hour
- Not producing bile
- Requirement for >60mls 8.4% NaHCO₃ in first 4 hours of perfusion

Bile

- pH<7.5
- Bile glucose >2.0mmol/L or <10mmol/L less than perfusate

The above criteria reveal an area of uncertainty with livers between the definitely usable and definitely unusable. There are currently no internationally accepted viability criteria, but those proposed by ourselves are in accord with most other criteria, and are based on the largest published experience to date^{14,15}. That said, a recent case, and the reason for amendment 5, has suggested that assessment at 2 or 4 hours may be too soon and a longer period of perfusion may be advisable in some livers to distinguish between a liver that will not recover, and one that is stunned and recovers after 4 hours.

5.8.1.2 *Livers outside criteria with late recovery of function*

Where the criteria are outside those favouring transplantation, but the liver appears to recover function as perfusion continues, a decision to use the liver will be taken in consultation with a member of the transplant team who is not involved in the research (typically both the on call hepatologist and surgeon), and the appropriateness of the proposed recipient will also be reviewed. It may be necessary to change recipient if there remains doubt over the liver

5.8.1.3 *Change of recipient after liver treatment has begun*

Any decision to change recipient will need to go through the national liver offering protocol, that is, it will need to be offered back to all other centres as a “Fast Track” offer and only if they decline its use can it be reallocated locally (unless it was originally accepted as a Fast Track with no named recipient when there is no need to offer the liver back).

If the liver is declined by all centres above Cambridge on the Fast Track offering, then the second recipient will be the person deemed most appropriate on clinical grounds by the medical team (hepatologist and surgeon) on call. If either of the individuals are study members, then someone outside the study should be involved in their stead. The second

recipient should be informed that the liver has been treated as part of the study, as well as being informed of the suboptimal nature of the perfusion parameters and the risk that using the liver for transplantation entails, that is, the risk that it may not function satisfactorily or at all.

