5.3 Number of Subjects

Around 60 transplant patients will be recruited. However, since approximately a third of DCD livers undergoing NESLiP will not pass viability criteria, approximately 45 DCD livers will need to be perfused. Similarly, around 15% of DBD livers undergoing perfusion do not pass viability criteria so around 35 DBD livers will need to be perfused.

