5.4 Sample size determination

Previous experience with back-to-base perfusion of DCD livers has been associated with a 20% incidence of anastomotic strictures and a 20% incidence of non-anastomotic bile duct strictures (unreported Cambridge data). In a cohort of 20 patients receiving a DCD liver treated by NESLiP it is likely that one will die, five will undergo retransplantation and four will develop non-anastomotic strictures. Similarly, the incidence of non-anastomotic strictures in DBD livers undergoing NESLiP in Cambridge is 8%, with a further 15% suffering anastomotic strictures.

A sample size of 30 DBD and 30 DCD should allow us to evaluate the safety of this therapy. It may also help determine whether the thrombolytic regimen increases the proportion of perfused livers that get transplanted and abolishes non-anastomotic strictures, and therefore whether it is worth proceeding to a formal randomised study and how to power that study

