5.6 Study endpoints

5.6.1 *Primary endpoint*

- Post reperfusion intra-operative blood loss
- Feasibility of adding TPA and FFP to livers undergoing normothermic perfusion before transplantation

5.6.2 *Secondary endpoint*

- Return to theatre in first 24 hours for bleeding
- Total and post reperfusion intra-operative blood transfusion
- Liver utilisation: proportion of liver perfusions resulting in a transplant
- Incidence of symptomatic anastomotic and non-anastomotic strictures at 6 months post-transplant
- Incidence of any anastomotic or non-anastomotic stricture excluding those related to hepatic artery thrombosis
- Incidence of “clinically relevant” non-anastomotic strictures, using the van Rijn definition¹¹
- Incidence of post reperfusion syndrome: 30% fall in mean BP lasting at least a minute in the first 5 minutes post reperfusion or the need for adrenaline or doubling of noradrenaline to support the circulation.
- Early allograft function (Olthoff criteria¹² and MEAF score¹³)
- Incidence of hepatic artery thrombosis in the first 6 months
- Incidence of acute kidney injury (RIFLE criteria)
- D-dimer release into perfusate compared to controls

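### The bile glucose entries favouring use and non-use of a liver (Protocol 5.8.1.1) overlap, so the same pair of readings can satisfy both, and nothing says which prevails

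*Protocol*

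**What the plan says.** Protocol 5.8.1.1 sets out two lists of seven items each. The first is introduced by "Criteria favouring transplantation of liver include" and has, for bile glucose, "Bile glucose <2.0mmol/L or >10mmol/L less than perfusate". The second is introduced by "Criteria favouring non-use of liver include" and has, for the same measurement, "Bile glucose >2.0mmol/L or <10mmol/L less than perfusate".

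After the lists the protocol comments: "The above criteria reveal an area of uncertainty with livers between the definitely usable and definitely unusable". It adds that no internationally accepted viability criteria exist and that some livers may need longer assessment. Section 5.8.1.2 deals with livers outside the use criteria that recover late. Neither section says what to do when one item points both ways.

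The decision to use a liver feeds an endpoint. Section 5.6.2 lists "Liver utilisation: proportion of liver perfusions resulting in a transplant" as secondary, and section 5.4 hopes to learn "whether the thrombolytic regimen increases the proportion of perfused livers that get transplanted". Section 5.3 speaks of livers passing or failing: "approximately a third of DCD livers undergoing NESLiP will not pass viability criteria".

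**The concern.** A pair of entries for use and non-use should be mutually exclusive. They may leave a zone between them where judgement applies, but one set of readings should not satisfy both. The bile glucose pair fails that test, and the uncertainty that the protocol acknowledges is of a different kind: it describes livers that fall between the entries, not livers that fall under both.

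Two things are at stake. First, staff at three centres (5.2) can take the same two readings, reach opposite conclusions on this item and each cite the protocol. The trigger in 5.8.1.2 for consulting someone outside the research team, which depends on a liver being outside the use criteria, is also unclear on this item. Second, the study is open label (5.1) and has no external supervision of its processes (10.7). A criterion that supports either answer may add to differences in acceptance between sites and between arms, and so to noise or drift in liver utilisation.

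**Working it through.** **Inputs.** Let B be bile glucose and P perfusate glucose, in mmol/L. All thresholds come from Protocol 5.8.1.1. The plan states no figure for the overlap, so there is none to reproduce. The only figures tied to viability, in 5.3, do reproduce: 30/(1 − 1/3) = 45 DCD perfusions, and 30/0.85 = 35.3, stated as about 35 DBD perfusions.

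**The two entries as written**

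- Use: B < 2 or P − B > 10.
- Non-use: B > 2 or P − B < 10.

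**Step 1: are they opposites?** The negation of the use entry is B ≥ 2 *and* P − B ≤ 10. The non-use entry has *or* in that place, so it also takes in livers that the use entry already covers.

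**Step 2: the four combinations**

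| Bile limb | Difference limb | Example (B, P) | P − B | Use entry | Non-use entry |
|---|---|---|---|---|---|
| B < 2 | P − B > 10 | 1.5, 20 | 18.5 | met | not met |
| B < 2 | P − B < 10 | 1.5, 9 | 7.5 | met | met |
| B > 2 | P − B > 10 | 5, 20 | 15 | met | met |
| B > 2 | P − B < 10 | 5, 9 | 4 | not met | met |

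Two of the four combinations satisfy both entries. A liver meets neither entry only at B = 2 and P − B = 10 exactly (P = 12), so in practice there is no gap.

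**Step 3: a consequence at low perfusate glucose.** If P < 10, then P − B < 10 whatever B is. The non-use entry is then always met, and no liver can meet the use entry alone.

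**Step 4: comparison with the other numeric pairs**

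| Item | Favours use | Favours non-use | Between them |
|---|---|---|---|
| ALT | < 6000 | > 10000 | gap |
| Lactate at 2 hours | < 2 | > 2.5 | gap |
| 8.4% bicarbonate, first 4 hours | < 40 ml | > 60 ml | gap |
| Bile pH | > 7.6 | < 7.5 | gap |
| Bile glucose | two limbs, *or* | two limbs, *or* | overlap |

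Bile glucose is the only numeric pair that overlaps.

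**Step 5: how often would it happen?** The documents give no distribution of B or P. Purely as an illustration, assume P uniform over a range and B uniform from 0 to P. The simulated share meeting both entries is then:

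- P 2–10: 40%
- P 5–15: 19%
- P 10–20: 21%
- P 10–30: 36%
- P 20–40: 58%

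The answer depends heavily on the assumption. None of these is an estimate for this trial.

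**The case against.** The strongest reply is that the lists are not a decision rule. They are criteria that favour one course or the other, each has seven items, and no number or combination of items is required. A liver with ALT below 6000 and lactate above 2.5 already has an entry on each list, with bile glucose playing no part. Discretion, and the risk that an unblinded team exercises it differently by arm, would remain after the wording is corrected. There is also partial protection: 5.8.1.2 and 5.8.1.3 bring in clinicians outside the study for late-recovering and reallocated livers. Utilisation is one of eleven secondary endpoints, and 5.4 says only that the sample may help to assess it. With one transplanted liver in six a control (section 7), or about 60/6 = 10, any comparison between arms will be imprecise anyway.

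All of this stands, and it limits the consequence. It does not make the two entries coherent. Conflict between two different measurements is what judgement is for. Here one measurement is assigned to both sides at once.

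A reader might also say that the intended meaning is obvious. It is not. Reading *and* into the non-use entry puts every overlapping liver on the use side, while reading *and* into the use entry puts every one on the non-use side. The limbs might also be meant for different perfusate glucose levels, but no such condition is stated.

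Three stronger inferences are tempting and are not supported:

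- That many livers are affected. Two of four logical combinations is not a proportion of livers.
- That such a liver meets both lists. It meets both bile glucose entries, and one entry does not decide a list.
- That utilisation loses a consistent rule. There was no strict rule to lose.

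**Conclusion.** The point holds as an internal contradiction in one acceptance criterion. It rests on the two entries as printed and on logic, with no distributional assumption. Two of the four limb combinations satisfy both entries, and no text resolves the conflict.

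The effect on the trial cannot be quantified from the documents. It is best described as contradictory guidance on one item of a discretionary assessment, which may contribute to inconsistent acceptance across sites and arms and so to the secondary endpoint of liver utilisation. The documents do not show that utilisation is biased, nor that correcting this item would remove the open-label risk. The correction is still worth making: the error is plain, it bears on whether an organ is regarded as usable, and it costs almost nothing to remove.

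**What to change.** The sponsor should reconcile the two bile glucose entries in 5.8.1.1 so that no pair of bile and perfusate readings can satisfy both. Logically, either of two forms does this: entries that are exact complements (overlap zero, no gap), or entries that leave a gap as the other numeric pairs do. Which wording, thresholds and direction hold is for the clinical team, and this review takes no position on them. The reconciled wording should go to all participating centres.

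The cost is a short protocol correction. It needs no new measurement and no change to the sample size or the analysis.

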10.4	Response criteria	20
10.5	Statistical methods to be employed.....	22
10.6	Analysis plan.....	22
10.7	Trial supervision	22
11	Assessment of Safety	22
11.1	Definitions.....	22
11.2	Expected adverse drug reactions.....	23
11.3	Expected Serious Adverse Events	23
11.4	Recording and evaluation of adverse events.....	24
11.5	Reporting adverse events	24
11.6	Reporting of Suspected Unexpected Serious Adverse Reactions (SUSARs)....	24
12	Data handling and record keeping	25
13	Direct access to source data / documents.....	25
14	Publications policy	26
15	Finance	26
16	Ethical considerations.....	26
16.1	Consent	26
16.2	Ethical committee review	26
16.3	Declaration of Helsinki and ICH Good Clinical Practise	26
17	Regulatory approval	26
18	References	26
19	Appendix 1. Rationale for change of infusion regimen.	28

1 Study Synopsis

Title of clinical trial	A pilot study of thrombolysis during machine perfusion of circulatory death donor livers to prevent biliary strictures
Short title	Thrombolysis during machine perfusion of DCD donor livers
Sponsor name	Cambridge University Hospitals NHS Foundation Trust and the University of Cambridge
IRAS project number	297403
Sponsor number	A095973
Trial registry Reference number	ISRCTN
REC number	21//EE/0237
Medical condition or disease under investigation	Cholangiopathy in livers removed from donors following circulatory or brain death
Purpose of clinical trial	To assess whether a thrombolytic regimen during ex situ normothermic liver perfusion can prevent biliary strictures
Primary objective	To evaluate the safety and feasibility of adding fresh frozen plasma and TPA to the perfusate
Secondary objective (s)	Prevention of biliary strictures (cholangiopathy) Improved liver graft function
Study Design	Pilot study ascending dose three-arm randomised unblinded study
Study Endpoints	Bleeding intra-operatively Feasibility of treating livers with TPA. Return to theatre within 24 hours for bleeding Incidence of anastomotic and non-anastomotic strictures
Sample Size	60 liver recipients
Summary of eligibility criteria	Adults undergoing a deceased donor liver transplant from a donor after circulatory death
Investigational regimen	Tissue plasminogen activator (alteplase) with fresh frozen plasma added to the perfusate ex situ .
Route(s) of administration	Ex situ (ex vivo) into the perfusate of a liver undergoing ex situ perfusion

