5.1 Statement of design

This is a three arm open label pilot study

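### Liver utilisation rests on a discretionary use decision in an open-label trial, so knowledge of the arm could shift it in either direction without a treatment effect

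*Protocol*

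**What the plan says.** - **Endpoint.** Protocol section 5.6.2 lists "Liver utilisation: proportion of liver perfusions resulting in a transplant" as one of 11 secondary endpoints. Section 10.3 says that TPA perfusions and the number of transplants will be compared with the control perfusions.
- **Use of the result.** Section 5.4 says of the sample: "It may also help determine whether the thrombolytic regimen increases the proportion of perfused livers that get transplanted". It couples this with abolishing non-anastomotic strictures, "and therefore whether it is worth proceeding to a formal randomised study".
- **Blinding.** Section 5.1: "This is a three arm open label pilot study". The synopsis agrees: "Pilot study ascending dose three-arm randomised unblinded study".
- **Viability criteria.** Section 5.8.1.1 gives one list favouring use and one favouring non-use, with no rule on how many items must be met. It then concedes: "The above criteria reveal an area of uncertainty with livers between the definitely usable and definitely unusable".
- **Outside input.** Under section 5.8.1.2, when a liver is outside the use criteria but appears to recover as perfusion goes on, a "decision to use the liver will be taken in consultation with a member of the transplant team who is not involved in the research". Section 5.8.1.3 also calls for someone outside the study, but for choosing a second recipient.

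**The concern.** Utilisation is not a measurement on the liver. It is the outcome of a decision, and the protocol leaves part of that decision to judgement. Where the criteria do not settle the matter, whoever decides may know whether the liver received TPA or FFP alone. Belief that TPA has cleared the peribiliary vessels could favour acceptance. Caution about bleeding after a novel thrombolytic treatment could favour refusal. Either way, utilisation could differ between arms with no effect of TPA.

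Two things are at stake. The first is a result that section 5.4 ties to the case for a larger trial. The second is the make-up of the recipient groups. If marginal livers are accepted at different rates by arm, early function, strictures and blood loss are compared between different mixes of livers. Matching in section 10.6 is on agonal phase duration, cold ischaemia time and the UK donor liver index. None of these describes performance on the machine, so matching would not correct this selection.

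**Working it through.** **1. The plan's own figures.** Section 5.3 gives non-use of about one third (DCD) and 15% (DBD), and sections 5.3 and 10.2 give the perfusions needed.
- DCD: 30 / (1 − 1/3) = 45.0; the protocol says about 45.
- DBD: 30 / (1 − 0.15) = 35.3; the protocol says about 35.

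Both are reproduced. Expected utilisation is therefore about 67% (DCD), 85% (DBD) and 60/80 = 75% overall.

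**2. Control perfusions.** Section 7 makes one transplanted liver in six a control. Assuming the same utilisation in both arms:
- DCD: 45/6 = 7.5 control and 37.5 TPA perfusions. One decision moves control utilisation by 100/7.5 = 13.3 points and TPA utilisation by 100/37.5 = 2.7 points.
- DBD: 35/6 = 5.83 control and 29.17 TPA perfusions. One decision moves control utilisation by 100/5.83 = 17.1 points and TPA utilisation by 100/29.17 = 3.4 points.

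**3. Where discretion lies.**
- Values between the two lists in section 5.8.1.1: ALT 6000–10000, lactate 2–2.5 at 2 hours, bicarbonate 40–60 ml, bile pH 7.5–7.6.
- The bile glucose items overlap. A value above 2.0 mmol/L but more than 10 mmol/L below perfusate satisfies an item on each list. The two items need to be reconciled.
- The outside clinician in section 5.8.1.2 is required only after apparent recovery, is consulted rather than made the decision-maker, and is not said to be unaware of the arm.
- No section keeps the allocation from anyone. Section 8.2 puts an alteplase syringe on a driver at the circuit and describes no dummy syringe for FFP-only livers.

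**4. Illustration of size (assumed inputs).** False difference = g × d, where g is the grey-zone share and d is the difference between arms in the proportion of grey-zone livers used. The protocol gives neither. Assume g = 10% to 30% and d = 20 to 60 points:
- smallest: 0.10 × 0.20 = 2 points
- middle: 0.20 × 0.40 = 8 points
- largest: 0.30 × 0.60 = 18 points

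From a DCD control value of 67%, TPA utilisation would appear as 69% to 85% if bias favours use, or 65% to 49% if it favours refusal.

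**5. What such a bias would look like.** Take 37 TPA and 8 control DCD perfusions as independent binomials with true control utilisation of 2/3. This is an approximation, because allocation is fixed on transplanted livers rather than on perfusions. The chance of observing a difference of at least 10 points in favour of TPA, with no treatment effect, is:
- no bias: 29%
- 8-point upward bias: 46%
- 18-point upward bias: 66%

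Fisher's exact test, named in section 10.5, gives p ≤ 0.05 in 3% (no bias) to 18% (18-point bias) of such trials. The exact 95% interval for 5/8 controls transplanted runs from 24% to 91%.

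**The case against.** **The gap is narrower than it looks.** A grey-zone liver is by definition outside the use criteria, so one accepted because it improved is already covered by section 5.8.1.2. This stands. What remains is livers accepted or declined without apparent recovery, and the protocol does not say how many there are. Even for the covered livers, consultation without masking limits the bias but does not remove it.

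**The decision-maker is not named.** A reader might infer that arm-aware investigators decide on ordinary grey-zone livers and will favour TPA. The protocol says neither. It is silent on who decides, and nothing indicates which way a bias would run. What can be said is that the design is open and no rule prevents arm knowledge from entering the decision.

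**Utilisation does not decide whether the programme goes on.** A reader might treat it as a go/no-go criterion. Section 5.4 says only that the sample may help, sets no threshold, and pairs utilisation with strictures. The primary objective is safety and feasibility.

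**Sparse controls are the larger weakness.** With 7 or 8 DCD control perfusions, a 10-point difference in favour of TPA arises by chance 29% of the time even without bias. This also stands: masking would not make the comparison precise. But imprecision is visible in a confidence interval, whereas differential acceptance is not, and it also affects who enters the recipient comparisons.

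**Full masking is impractical.** The infusion set-up shows the arm to anyone at the machine, and handing the decision to clinicians unaware of treatment would alter clinical responsibility. This is accepted, and the remedy is limited accordingly.

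**Conclusion.** The concern holds in a limited form. As written, the protocol lets knowledge of the arm influence an endpoint that is itself a human decision, and its only safeguard on the use decision covers some of the livers at issue and does not mask the arm. Utilisation could shift up or down without a treatment effect, and the livers reaching recipients could differ by arm.

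The size cannot be derived from the document. The 2 to 18 points above are the product of assumed inputs and should not be read as an estimate. What does follow from the protocol, assuming equal utilisation in the arms, is fragility: one decision on a control liver moves control utilisation by about 13 points (DCD) or 17 points (DBD).

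A false significant result is not the main danger, since the test would rarely reach significance. The danger is a misleading descriptive signal in a pilot whose results will be read descriptively. The change is worth making but does not threaten the primary safety objective.

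**What to change.** 1. For every perfused liver, record before the use decision which listed criteria were met, not met or not assessable, and record the reason for use or non-use with the decision. The third category is needed because a liver without bile has no bile pH or glucose, and one removed soon after the 2-hour minimum (section 2.9) has no 4-hour bicarbonate total.
2. For livers that miss a use criterion but are being considered for transplantation, obtain the opinion of the on-call clinicians outside the research already named in section 5.8.1.2. Give it from the perfusion record, without stating the arm where practicable. The final decision, the recipient team's access to the allocation and the viability criteria stay as they are.
3. Report utilisation for all perfused livers by randomised arm, split into livers meeting all use criteria, other livers accepted and other livers declined. Show alongside it the proportion meeting all use criteria, which does not depend on the use decision.

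The trigger in item 2 should not be failure to meet all non-use criteria. No liver can meet them all, because absence of bile and the bile measurements exclude one another.

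Cost: protocol wording, a short extra record per liver, and some call on outside clinicians where those on duty are study members. Masking will be imperfect, but the record alone would expose differential acceptance.
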